PRINCIPAL/OVERALL INVESTIGATOR

[name]

PROTOCOL TITLE

A smartphone-based application post-myocardial infarction to manage cardiovascular disease risk

FUNDING

Boston Scientific

VERSION DATE

02/26/2019

I. SPECIFIC AIMS

Specific Aim 1: To recruit and onboard 100 patients sustaining a myocardial infarction and 50 patients with symptomatic coronary artery disease without myocardial infarction who have undergone PCI with the Wellframe patient engagement platform. Patients will be recruited during index cardiac hospitalization in the inpatient setting.

Specific Aim 2: To determine feasibility of inpatient onboarding of the Wellframe patient engagement platform in the setting of acute myocardial infarction. We will evaluate process outcomes, including proportion of eligible participants agreeing to participate, survey completion rates, content engagement, patient application engagement, and patient satisfaction scores.

Specific Aim 3: To assess the clinical efficacy of the Wellframe patient engagement platform post-myocardial infarction compared to matched historical controls. We will also evaluate outpatient clinic follow-up rates after hospitalization as well as cardiac rehabilitation enrollment rates (primary outcome) for all participants. We will evaluate 90-day and 30-day readmission and ED visit rates for post-myocardial infarction participants.

We hypothesize that the patient engagement platform will be an efficient method for cardiology staff to engage, follow-up, and educate patients peri-percutaneous coronary intervention (PCI) in the setting of acute myocardial infarction.

II. BACKGROUND AND SIGNIFICANCE

Public Health Significance

Myocardial infarction is a leading cause of morbidity and mortality in the United States and worldwide.^{1,2} Acute management of myocardial infarction involves pharmacological and revascularization strategies to reduce recurrent ischemic events, including cardiovascular death.^{3,4} Secondary prevention measures include adherence to guideline-based pharmacologic strategies, management of cardiovascular risk factors, diet and lifestyle counseling, and participation in cardiac rehabilitation. Both patient- and treatment-specific factors are associated with short-term adverse events.

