The Health Advocate builds a supportive, coaching relationship with the patient and provides non-clinical support, encouragement, and accountability to maximize engagement. The Health Advocate sends encouraging messages and addresses patients’ non-clinical needs, facilitates patient adherence to care programs, promotes patient program retention and engagement through multiple communication channels, and monitors the patients’ Mobile App behaviors. As a part of these activities, the Health

Advocate directly encourages patients to complete the tasks in their Wellframe care program, including reading their health education and completing their surveys.

The Health Advocate co-manages patients with the clinical team via the Wellframe dashboard. The Health Advocate facilitates triage of clinical needs to clinical staff. As a non-clinician, the Health Advocate operates under the supervision of Wellframe's team of licensed clinicians (physicians and nurse practitioners), and all patient communication adheres to structured protocols and guidelines set forth by Wellframe clinical leadership.

III. RESEARCH DESIGN AND METHODS

Sample size: 150 post-PCI at Massachusetts General Hospital (MGH) and Brigham & Women's Hospital (BWH): 100 with myocardial infarction, 50 with symptomatic coronary artery disease without myocardial infarction

Inclusion/Exclusion Criteria

- Acute myocardial infarction – defined by typical symptoms, characteristic kinetics of cardiac biomarkers or characteristic EKG changes

Or

Symptomatic coronary artery disease without myocardial infarction – defined by typical symptoms (i.e. angina) and signs (i.e. abnormal non-invasive cardiovascular testing: stress testing or coronary CTA)

Inclusion Criteria

- Age 21-85
- English-speaking
- PCI: balloon angioplasty, bare-metal stent, or drug-eluting stent at MGH
- Smartphone or Tablet (iOS or Android)
- Long term provider in Massachusetts (or records available through Care Everywhere)

Exclusion Criteria

- Recent (within 1mo) illicit substance use or alcohol abuse
- In-hospital AMI
- Known pregnancy
- Dementia or cognitive disability
- Incarceration

Study Outcomes

Clinical and Utilization Outcomes

Clinical outcomes will be ascertained from electronic medical records. Patients will also be called at 90 days to determine potential readmission, representation, and cardiac rehabilitation enrollment at other hospitals or clinics during the follow-up period. The following outcomes will be assessed:

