- Utilization and Attendance
 - 4 Week Follow-up Appointment: % of patients who attend cardiology follow-up appointments after PCI
- **Readmission Rates**
 - **30 Days- Primary Outcome**
 - 60 Days
 - **90 Days – Secondary Outcome**
- Representation Rates (ED presentation with hospitalization)
 - 30 Days
 - 60 Days
 - 90 Days
- **Enrollment in clinic-based cardiac rehab**
 - **% of patients discharged after intervention who attend at least one session of clinic-based cardiac rehab -Secondary Outcome**
- Cost Effectiveness

[figure not shown]
Process Outcomes

These data will be provided by Wellframe to the PI. “Conversion rate” will be the primary outcome as this will indicate patient acceptability of initiating the platform and the remainder listed below will be secondary outcomes. The proportion of individuals with cardiovascular disease who accept a smartphone application upon discharge is largely an outstanding question. We hypothesize that >50% of eligible and recruited patients will enroll in the Wellframe app. Data from Wellframe will be used to assess:

- Conversion Rate: Number of patients who enroll in Wellframe app out of the number of patients eligible for participation
- Medication Adherence: % of medication reminder tasks that were completed
- Content Completion: % of content tasks that were completed
- Survey Completion: % of survey tasks that were completed
- Patient Engagement:
 - % Weekly engagement (percent of days in which patient had engaged at least once over the previous 7 days)
 - % Daily engagement (percent of days in which patient had engaged)
- Patient Messaging:
 - Number of messages sent
 - Percent of messages sent to patients that were opened at any point
 - Percent of messages sent to patients that had at least one message from the patient afterwards
- Patient Satisfaction: average response to patient satisfaction questions asked through app’s survey functionality
- Patient Physical Activity
- Clinical Messaging:
 - Total number of messages sent
 - Percent of patients who received at least one message

Primary and secondary outcomes are labeled and in bold, all other outcomes are exploratory outcomes.

Schema

■ Subject Enrollment

■ Study Procedures

■ Study Closeout and Post Study Follow-up

Subject Enrollment

Overview

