We hope that this study will help us better understand and improve prevention of recurrent atherosclerotic cardiovascular disease (ASCVD) events after a myocardial infarction, through patient specific factors. During the time between when a patient leaves the hospital and attends their follow-up appointments it is critical for patients to comply with the diet and exercise advice given to them, and take their medications as prescribed. This study will help us better understand patient compliance with these activities when they leave the hospital, and guide future studies on patient mobile health application usage. We hope this study will also lead to development of better strategies to coordinate care between the time of discharge and the next follow up appointment. Potential benefits to subjects from this study would include increased medication adherence, and better adherence to health behaviors associated with decreased cardiovascular disease risk.

VII. POWER ANALYSIS

We plan to compare 30 day readmission rates amongst study participants to historical controls. We will match subjects to controls based on age +/- 5 years, sex, and insurer (commercial, non-commercial). Controls will be gathered through RPDR. Identified data sets may be used to conduct chart review of controls.

We have at least 80 percent power with 150 enrolled participants, 600 matched historical controls, with alpha equal to 0.05, to detect an effect of at least 2.5-fold for the primary clinical outcome, likelihood of readmission to the hospital during the 30 day study period with 5% readmission rates.

VIII. REFERENCES

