D.8. Sample size and power: We have at least 95 percent power with 150 enrolled participants, 450 matched historical controls, with alpha equal to 0.05, to detect an effect of at least 2-fold increase in the primary clinical outcome, likelihood of enrollment in cardiac rehabilitation within the 90 day study period with baseline 25% enrollment rates⁶.

E. General Considerations:

E.1. Analysis populations:

E.1.a.: Full analysis population: All intervention subjects who downloaded the study application and 3:1 matched historical controls.

E.1.b.: Engagement population: All intervention subjects who downloaded the study application.

E.2. Covariates and subgroups: Sex (M/F), State (MA/non-MA), PCI Type (MI/Elective), DM2 (Y/N), Partners PCP (Y/N), Insurance Type (Commercial/Medicaid/Medicare/Other)

E.3. Missing data: Missing data values for participants who fit inclusion criteria will default to zero or “no” for dichotomous variables. Missing data values for participants will default to “unknown” or “other” for continuous or categorical variables.

F. Summary of study data: All continuous variables will be summarized using the following descriptive statistics: n (non-missing sample size), mean, standard deviation, median, maximum and minimum. The frequency and percentages (based on the non-missing sample size) of observed levels will be reported for all categorical measures. In general, all data will be listed, sorted by site, treatment and subject, and when appropriate by visit number within subject. All summary tables will be structured with a column for each treatment in the order (Control, Experimental) and will be annotated with the total population size relevant to that table/treatment, including any missing observations.

G. Protocol deviations: Subjects who do not fit inclusion criteria will be removed from the data set prior to analysis. Subjects with missing data will be treated as discussed above (Section E.3.)

H. Efficacy Analyses: The Cox Proportional Hazards model will be used to assess efficacy of the intervention (use of the application) on the primary outcome. The percentage of subjects attending cardiac rehabilitation enrollment within 90 days of discharge from incident PCI hospitalization will be compared across groups. A secondary analysis between the two groups will be conducted adjusting for covariates such as age, sex, insurance type, state, diabetes, and partners PCP).

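### Protocol VII claims at least 80% power for 30-day readmission without saying which group has the 5% rate or which direction is meant; if 5% is the control rate, a 2.5-fold reduction has about 32% power

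*Protocol*

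**What the plan says.** Protocol VII is the Protocol's only power statement. It reads "We have at least 80 percent power with 150 enrolled participants, 600 matched historical controls, with alpha equal to 0.05", for an effect of 2.5-fold or more on what it calls the primary clinical outcome: "likelihood of readmission to the hospital during the 30 day study period with 5% readmission rates". It gives no direction, no ratio scale, no sidedness and no test, and does not attach the 5% to a group.

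Other places bear on the same sentence:

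- Protocol III, Study Outcomes, labels readmission "30 Days- Primary Outcome".
- Protocol I, Specific Aim 3, gives the primary label to "cardiac rehabilitation enrollment rates (primary outcome) for all participants". On readmission it says: "We will evaluate 90-day and 30-day readmission and ED visit rates for post-myocardial infarction participants".
- Protocol III, Sample size, splits the 150 participants into "100 with myocardial infarction, 50 with symptomatic coronary artery disease without myocardial infarction".
- SAP D.8 powers rehabilitation enrolment, not readmission, with "150 enrolled participants, 450 matched historical controls, with alpha equal to 0.05". It specifies an increase and labels its rate: "within the 90 day study period with baseline 25% enrollment rates".
- SAP E.1.a sets 3:1 matching. SAP J uses Cox models to look for lower hospitalization rates. SAP K makes rehabilitation enrolment the only primary outcome and everything else exploratory.

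**The concern.** A fold change and one event rate do not fix the power until the reader knows whose rate it is and which way the effect runs. Here that choice moves the power from about one third to above four fifths.

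The reading that comes first to mind for an app meant to keep patients out of hospital is a 5% background rate and a reduction. It is also the reading on which the stated power is not delivered. A null readmission result could then be presented, with section VII as support, as fair evidence of no 2.5-fold benefit when the comparison had little chance of showing one.

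**Working it through.** **Inputs.** App group n₁ = 150, controls n₂ = 600, alpha 0.05, effect 2.5-fold, rate 5% (all Protocol VII). Controls n₂ = 450 (SAP D.8). Assumptions: risk-ratio scale, independent groups (matching ignored), and two-sided unless stated.

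**Formula.** Two-proportion test with pooled null variance: power = Φ[(|p₁ − p₂| − z·SE₀)/SE₁], where SE₀ = √(p̄(1 − p̄)(1/n₁ + 1/n₂)), SE₁ = √(p₁(1 − p₁)/n₁ + p₂(1 − p₂)/n₂), p̄ is the weighted mean rate, and z = 1.96 (1.645 one-sided).

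**Step 1: reproduce the plan's figure (150 vs 600).** Controls 12.5%, app 5%:

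- p̄ = (7.5 + 75)/750 = 0.110; SE₀ = 0.02856; SE₁ = 0.02234.
- (0.075 − 0.05598)/0.02234 = 0.851, so power is **80.3%**.

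The stated figure is therefore obtainable, with the 5% in the app group.

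**Step 2: 5% as the control rate, reduction to 2%.**

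- p̄ = (3 + 30)/750 = 0.044; SE₀ = 0.01872; SE₁ = 0.01449.
- Two-sided: (0.030 − 0.03670)/0.01449 = −0.462, so power is **32.2%**.
- One-sided: (0.030 − 0.03080)/0.01449 = −0.055, so power is 47.8%.

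**Step 3: 5% as the control rate, increase to 12.5% (harm).**

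- p̄ = (18.75 + 30)/750 = 0.065; SE₀ = 0.02250; SE₁ = 0.02843.
- (0.075 − 0.04411)/0.02843 = 1.087, so power is **86.1%**.

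**Step 4: all four readings, two-sided pooled test.**

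| Control → app | 600 controls | 450 controls |
|---|---|---|
| 5% → 2% (reduction) | 32.2% | 31.8% |
| 12.5% → 5% (reduction) | 80.3% | 77.7% |
| 5% → 12.5% (increase) | 86.1% | 83.6% |
| 2% → 5% (increase) | 53.3% | 49.5% |

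The choice of reading drives the spread. Moving from 600 to 450 controls costs at most about 4 points.

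**Step 5: does the method rescue 5% → 2%?** With 600 controls, exact chi-squared gives 34.1%, Fisher 32.6%, simulated log-rank about 33% and simulated Cox Wald 17.6%. The most favourable approximation tried is Schoenfeld's:

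- Expected events 3 + 30 = 33; log hazard ratio = ln[ln(0.98)/ln(0.95)] = −0.932.
- 0.932 × √(33 × 0.2 × 0.8) = 2.141.
- Power is Φ(2.141 − 1.960) = 57% two-sided and Φ(2.141 − 1.645) = 69% one-sided.

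Reading 2.5-fold as an odds ratio gives 30.7% (two-sided pooled). None reaches 80%.

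**Step 6: is the 78% robust?** No. For 12.5% → 5% with 450 controls, two-sided results are 77.2% (Fisher), 77.6% (simulated Cox Wald), 78.6% (exact chi-squared), 82.2% (arcsine), 82.3% (exact likelihood ratio), 88.7% (unpooled) and 91.1% (Schoenfeld). One-sided pooled is 87.5%.

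**Step 7: analysed group.** If readmission is assessed only in the 100 planned post-MI participants, and 300 to 600 controls and the same rates are assumed, the two-sided pooled power is 57% to 62% for 12.5% → 5% and about 20% for 5% → 2%. The control counts and rates are assumptions, so these figures only illustrate the size of the effect.

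**The case against.** The strongest reply is that section VII contains no arithmetic error. On its own 150 and 600, two readings satisfy the claim, and one of them is a benefit. A reader might infer that the sponsor miscalculated; the documents do not support that, because 80.3% matches the stated figure closely.

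A second reply is that the 32% rests on a reading the Protocol never states. The idea of 5% as a background rate comes from the form of SAP D.8, which concerns another outcome and an increase; following that sentence fully would give a 5% baseline, an increase, and 86%. The idea of a reduction comes from SAP J, an exploratory section. This stands: 32% is conditional, not a finding about the trial as designed.

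A third reply concerns the control count. A reader might infer that the SAP's 450 controls are what breaks the claim. They are not: the 78% is about two points short, and some tests, or a one-sided test, put it above 80%.

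Finally, the SAP is dated 12/28/19, after the follow-up it schedules to end in 09/2019, and it treats readmission as exploratory. A restated power cannot change enrolment or the confirmatory conclusion. That limits the impact, but it leaves the Protocol with a power claim and a primary label that conflict with its own Aim 3.

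**Conclusion.** The point holds as an undefined power claim whose undefined part decides the answer. If 5% is the control rate and a reduction is meant, power is about 32% two-sided or 48% one-sided, and no method tried reaches 80%. To support the stated figure as a benefit, the 5% must belong to the app group and controls must be near 12.5%, a rate that appears in neither document. With 5% in controls, the pooled test reaches 80% only for an effect in the harmful direction.

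These results assume a 2.5-fold risk ratio and ignore the matching. It would go too far to say that the trial has 32% power for readmission, or that 450 controls bring it below 80%.

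Two inconsistencies need no assumption. Section VII counts 150 participants where Aim 3 assesses readmission in the post-MI group (100 planned). Section VII and the outcome list also make readmission primary, where Aim 3 and the SAP make rehabilitation enrolment primary. The consequence is for how a readmission result is read, not for the SAP's primary analysis.

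**What to change.** Align the primary label in the Protocol's outcome list and section VII with Aim 3 and the SAP, and mark section VII as superseded by SAP D.8 for the primary outcome. That is enough if no power for readmission is to be claimed.

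If a readmission power is kept, withdraw the claim of at least 80% unless a 12.5% control rate is stated with its source. Give the rate in each group, the direction, the ratio scale, the sidedness, the test, the analysed group (all participants or post-MI only) and the current control count, with the power that follows. For 5% to 2% with all 150 participants, that is about 32% on a two-sided pooled test with either control count. A different test, such as the Cox model in the SAP, needs its own figure.

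The cost is wording only, with no extra enrolment. The downside is that the stated power may become less favourable.

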A Smartphone-based Application Post-myocardial Infarction to Manage Cardiovascular Disease Risk
NCT03416920
Version Date: 12/28/19
[name], [name]
Statistical Analysis Plan

A. Background and Rationale:

The period between inpatient hospitalization for symptomatic coronary artery disease (CAD) and post-discharge office consultation remains a vulnerable interval for adverse outcomes. We sought to develop and evaluate a tool to help guide, reassure and educate patients during this susceptible time.

We aimed to recruit and onboard 150 patients who have undergone percutaneous coronary intervention (PCI) with a novel mobile health platform developed specifically for this population. The mobile application (app) includes educational about specific procedures (PCI) and diagnoses (coronary artery disease, acute myocardial infarction) as well as lifestyle education programs (hypertension, hyperlipidemia, diabetes, weight loss, smoking cessation). The app also utilizes live health care coaches to interact with participants virtually to facilitate adherence to outpatient follow up, enrollment in cardiac rehabilitation and achieve individually targeted goals.

B. Hypothesis:

Our overall hypothesis is that engagement with our smartphone application post PCI will correlate with increased rates of enrollment in cardiac rehabilitation amongst study participants as compared to historical controls.

C. Endpoints:

- C.1. Primary:** 90-day cardiac rehabilitation enrollment rates
- C.2. Secondary:** 30-day cardiac outpatient follow up attendance

D. General Study Design and Plan

- D.1. Design:** Multi-site stratified single-arm prospective study

- D.2. Type of controls:** Historical

D.2.a. Control ascertainment: Query of Research Patient Data Registry (RPDR) database (a centralized clinical data registry that gathers clinical information from various Partners hospital systems with a query tool that provides users with detailed medical record information on identified patient populations that meet user-defined characteristics and criteria such as diagnoses, procedures, medications and/or laboratory results) for subjects aged 21-85 years old who underwent percutaneous coronary intervention from 01/01/2015 through 12/31/2017.

D.2.b. Control matching: Controls matched for Age, Sex (M/F), State (MA/non-MA), PCI Type (MI/Elective), DM2 (Y/N), Partners PCP (Y/N), Insurance Type (Commercial/Medicaid/Medicare/Other), Site (MGH/BWH)

- D.3. Level and method of blinding:** Open-label

- D.4. Randomization time point:** NA

- D.5. Timeframe of all study periods:**

D.5.a. Intervention arm: screening (02/2018-06/2019), baseline (02/2018-06/2019), intervention period (02/2018-09/2019), follow-up (05/2019-09/2019)

D.5.b. Historical control arm: baseline (01/2015-12/2017), follow-up (03/2015-03/2018)

D.6. Inclusion/Exclusion criteria:

D.6.a: Inclusion: 21-85 years old, fluency in English language, underwent PCI at either MGH or BWH during screening period for either symptomatic CAD or ACS, own a smartphone or tablet

D.6.b: Exclusion: Recent (<1mo) drug or alcohol abuse, in hospital AMI, pregnancy, cognitive delay/dementia, incarceration

D.7. Study variables:

Age	Age at time of enrollment into study as coded into Partners EHR
Sex	Gender as coded into Partners EHR
State	State of residence (Massachusetts vs Non-Massachusetts) at time of enrollment into study as coded into Partners EHR
PCI Type	Reason for percutaneous coronary intervention (PCI). Myocardial infarction (MI) coded as chart diagnosis of MI or positive serologic (troponin) values prior to PCI. All other PCI without evidence of myocardial necrosis coded as elective.
Partners PCP	Coded "yes" for patients with PCP in Partners EMR working primarily for Partners Healthcare system. Coded "no" for patients with PCP in Partners EMR not within Partners system or missing PCP data.
Insurance Type	Coded based on primary insurance listed in Partners EMR.
Site	Coded based on location of incident PCI procedure (either Massachusetts General Hospital [MGH] or Brigham and Womens Hospital [BWH])
Hypertension	Chart diagnosis of HTN prior to or at time of incident PCI
Hyperlipidemia	Chart diagnosis of HLD prior to or at time of incident PCI, LDL-C >129 at time of incident PCI or Triglycerides >150 at time of incident PCI
Type 2 Diabetes	Chart diagnosis of DM2 prior to or at time of incident PCI, or Hemoglobin A1c > 6.4 at time of incident PCI
Peripheral Arterial Disease	Chart diagnosis of PAD prior to or at time of incident PCI or history of peripheral arterial intervention
Smoking	Chart history of smoking (codified as current smoker, former smoker (quit >1 month prior to PCI), or never smoker). For analysis, variable was condensed into never smoker or ever smoker (either current or former).
Coronary Artery Disease	Chart diagnosis of CAD prior to or at time of incident PCI or history of CABG or prior PCI
30-day hospitalization	Admission date to a Partners hospital within 30 calendar days of incident PCI.
90-day hospitalization	Admission date to a Partners hospital within 90 calendar days of incident PCI.
Cardiac reason for hospitalization	Admission for chief complaint of cardiac etiology (ie CAD, CHF, arrhythmia), admission requiring cardiac consultation or admission to a cardiology ward unit.
30-day ER visit	Presentation to Partners ER or Urgent Care within 30 calendar days of incident PCI without subsequent hospitalization.
90-day ER visit	Presentation to Partners ER or Urgent Care within 90 calendar days of incident PCI without subsequent hospitalization.

90-day Cardiac Rehabilitation	Attendance of cardiac rehabilitation intake session at a Partners facility within 90 calendar days of incident PCI.
30-day Cardiac Follow Up	Attendance of cardiac outpatient follow up appointment at a Partners facility (with MD or NP) within 30 calendar days of incident PCI
30-day repeat PCI	Repeat percutaneous intervention on same or new coronary lesion within 30 days of incident PCI.
90-day repeat PCI	Repeat percutaneous intervention on same or new coronary lesion within 90 days of incident PCI.
90-day Stroke	Chart diagnosis of or admission for new stroke within 90 calendar days of incident PCI as noted in Partners EHR.
90-day Nonfatal MI	Chart diagnosis of or admission for myocardial infarction (without subsequent death) within 90 calendar days of incident PCI as noted in Partners EHR.
90-day CV Death	Documentation of death within 90 calendar days of incident PCI noted in Partners EHR with cause specified as secondary to CAD, CHF, Arrhythmia or other clear cardiovascular reason.
90-day All Cause Death	Documentation of death within 90 calendar days of incident PCI noted in Partners EHR.
Conversion Rate	Number of patients enrolled in Wellframe out of number of total patients eligible for study.
Days Enrolled	Number of days between patient onboarded with Wellframe app and marked done by clinical staff.
Medication Reminders	Number of medication reminders set up by patient (0 if patient has not set up any reminders).
30-day Medication Adherence	Percentage of medication reminder tasks completed within 30 days on app. (Null if no patient reminders set up)
90-day Medication Adherence	Percentage of medication reminder tasks completed within 90 days on app. (Null if no patient reminders set up)
30-day Content Completion	Percentage of content tasks (articles opened) completed within 30 days on app
90-day Content Completion	Percentage of content tasks (articles opened) completed within 90 days on app
30-day Survey Completion	Percentage of survey tasks completed within 30 days on app
90-day Survey Completion	Percentage of survey tasks completed within 90 days on app
30-day Weekly Patient Engagement	Percentage of days in which patient completed at least one task from the app checklist (survey, article, physical activity goal, encouragement) or sent a message to clinical team at least once over the previous 7 days within 30 days on app.
90-day Weekly Patient Engagement	Percentage of days in which patient completed at least one task from the app checklist (survey, article, physical activity goal, encouragement) or sent a message to clinical team at least once over the previous 7 days within 90 days on app.
30-day Daily Patient Engagement	Percentage of days in which patient completed at least one task from the app checklist (survey, article, physical activity goal, encouragement) or sent a message to clinical team within 30 days on app.

90-day Daily Patient Engagement	Percentage of days in which patient completed at least one task from the app checklist (survey, article, physical activity goal, encouragement) or sent a message to clinical team within 90 days on app.
Patient Satisfaction	Average patient response on app satisfaction via app survey function.
Patient Messages Sent	Number of total messages sent by patient within 90 days on app
Patient Messages Received	Number of total messages sent to patient within 90 days on app
Patient Messages Opened	Percentage of messages sent to patient that were opened
Patient Message Response	Percentage of messages sent to patient with at least one message response from patient
Patient Physical Activity	Percentage of days where patient met physical activity goal (default of 500 steps) within 90 days on app.
Days to First Message	Days until first message sent from care team to patient
Clinical Messages	Percentage of patients receiving at least one message from app care team within 90 days on app.

D.8. Sample size and power: We have at least 95 percent power with 150 enrolled participants, 450 matched historical controls, with alpha equal to 0.05, to detect an effect of at least 2-fold increase in the primary clinical outcome, likelihood of enrollment in cardiac rehabilitation within the 90 day study period with baseline 25% enrollment rates⁶.

E. General Considerations:

E.1. Analysis populations:

E.1.a.: Full analysis population: All intervention subjects who downloaded the study application and 3:1 matched historical controls.

E.1.b.: Engagement population: All intervention subjects who downloaded the study application.

E.2. Covariates and subgroups: Sex (M/F), State (MA/non-MA), PCI Type (MI/Elective), DM2 (Y/N), Partners PCP (Y/N), Insurance Type (Commercial/Medicaid/Medicare/Other)

E.3. Missing data: Missing data values for participants who fit inclusion criteria will default to zero or “no” for dichotomous variables. Missing data values for participants will default to “unknown” or “other” for continuous or categorical variables.

F. Summary of study data: All continuous variables will be summarized using the following descriptive statistics: n (non-missing sample size), mean, standard deviation, median, maximum and minimum. The frequency and percentages (based on the non-missing sample size) of observed levels will be reported for all categorical measures. In general, all data will be listed, sorted by site, treatment and subject, and when appropriate by visit number within subject. All summary tables will be structured with a column for each treatment in the order (Control, Experimental) and will be annotated with the total population size relevant to that table/treatment, including any missing observations.

G. Protocol deviations: Subjects who do not fit inclusion criteria will be removed from the data set prior to analysis. Subjects with missing data will be treated as discussed above (Section E.3.)

H. Efficacy Analyses: The Cox Proportional Hazards model will be used to assess efficacy of the intervention (use of the application) on the primary outcome. The percentage of subjects attending cardiac rehabilitation enrollment within 90 days of discharge from incident PCI hospitalization will be compared across groups. A secondary analysis between the two groups will be conducted adjusting for covariates such as age, sex, insurance type, state, diabetes, and partners PCP).

Primary analysis will verify balance in matching (unadjusted) via Chi-squared model for binary variables and ANOVA for categorical variables

I. Engagement Analyses: Overall engagement by patients in the intervention arm with the Wellframe application will be assessed by evaluating the number of days or weeks with at least one task completed (including surveys done, content read, activity goals reached and medication reminders used) within both a 30- and 90-day period. Individual task completion rates will also be assessed and reported within 30- and 90-day periods. Use of messaging between patients and health advocates will also be assessed during a 30- and 90-day period. Changes in these metrics across 30- to 90-days will be evaluated.

J. Exploratory Analyses:

We will compare subgroups (MI/elective) using linear regression across the 30-day engagement metrics above to evaluate predictors of engagement (adjusting for both 30-day engagement as well as matching covariates such as age, sex, PCI type, state, insurance, partners PCP and site).

We will use the Cox Proportional Hazards model to assess efficacy of the intervention on lowering rate of ER visits for cardiovascular reasons, ER visits for all causes and hospitalizations for all reasons.

We will use the Cox Proportional Hazards model to assess efficacy of the intervention on reducing rates of repeat PCI, stroke, non-fatal MI, cardiovascular cause of death and all cause death within 90 days of enrollment.

We will use the Cox Proportional Hazards model to assess for improvement in percentage of patients adhering to cardiovascular follow up appointments within 30 days of discharge.

K. Type I Error Control: We will control for error by limiting our primary outcome to 90-day cardiac rehabilitation enrollment. All subsequent analysis, including secondary outcomes, will be considered exploratory.

L. References:

